## 4.2 Objectives and Endpoints

Objectives	Endpoints
Primary	
The primary objective of this study is to determine the responder rate at higher infusion parameters of IgPro20 under the following conditions:	The primary endpoints are as follows: 
 
• Pump-Assisted Volume Cohort: Percentage of responders for each
 

Objectives	Endpoints

 
• Pump-Assisted: Volume per injection site of 25 mL, 40 mL, and 50 mL;
 
• Pump-Assisted: Flow rate per injection site of 25 mL/h, 50 mL/h, 75 mL/h and 100 mL/h;
 
• Manual Push (manual infusion using syringe without a pump): Flow rate per injection site of 30 mL/h, 60 mL/h, and 120 mL/h (0.5 mL/minute, 1 mL/minute, and 2 mL/minute, correspondingly).
 
	
planned volume (i.e., 25 mL, 40 mL and 50 mL per injection site).
 
 
• Pump-Assisted Flow Rate Cohort: Percentage of responders for each planned flow rate (i.e., 25 mL/h, 50 mL/h, 75 mL/h and 100 mL/h per injection site).
 
• Manual Push Flow Rate Cohort: Percentage of responders for each planned flow rate (i.e., 30 mL/h [0.5 mL/minute], 60 mL/h [1 mL/minute], and 120 mL/h [2 mL/minute] per injection site).
 

Secondary	

 
• To evaluate the safety of pump-assisted IgPro20 infusions at higher infusion parameters (volume and flow rate).
 
• To evaluate the safety of manual push IgPro20 infusions.
 
• To evaluate the tolerability of higher infusion parameters of IgPro20.
 
	
 
• The rate of total adverse events (AEs) per subject and per infusion by cohort and by each of the infusion parameter levels within the cohort.
 
• The rate of local reactions per subject and per infusion by cohort and by each of the infusion parameter levels within the cohort.
 
• The time to onset of local reactions per subject and per infusion by cohort and by each of the infusion parameter levels within the cohort.
 
• Severity of local reactions per subject and per infusion by cohort and by each of the infusion parameter levels within the cohort.
 
• Duration of local reactions per subject and per infusion by cohort and by each of the infusion parameter levels within the cohort.
 
• For all cohorts: Tolerability of a certain infusion parameter, i.e. percentage of infusions per cohort by volume/flow rate subgroup experiencing no severe local reactions for each of the infusion parameter levels.
 

Objectives	Endpoints
Exploratory	

 
CCI [REDACTED]
 
[REDACTED]
 
[REDACTED]
 
[REDACTED]
 
	
 
CCI [REDACTED]
 
[REDACTED]
 
[REDACTED]
 

[figure not shown]
### 4.3 Study Treatments

The study treatment, IgPro20 (trade name Hizentra®), will be manufactured by CSL and will be labelled as investigational medicinal product for this study.

The active substance is human normal immunoglobulin in a ready-to-use formulation for subcutaneous injection. The same dose as prescribed by the subject’s healthcare provider prior to study entry will be used throughout the study, usually within 100-200 mg/kg per week range.

Subjects will administer infusions following the schedule below:

**Figure 1 Study Flowchart**

Subjects in the Pump-Assisted Cohorts will administer weekly treatment and subjects in the Manual Push Cohort will administer frequent infusions (i.e., 2-7 times per week). Subjects in the Manual Push Cohort should maintain the same frequency of infusions per week throughout the whole study; including one month prior to Day 1 (date of Week 1 visit at the

site). The infusion parameters not under test (e.g., volume per injection site in the Flow Rate Cohort) should not exceed the levels used before the study.

#### **4.4 Randomization Procedures and Blinding**

This study is open-label and not randomized. Each study cohort requires specific entry criteria. However, these criteria are not mutually exclusive, and if a subject qualifies to be enrolled into more than one of the study cohorts, he/she may be assigned to either cohort at the investigator's discretion.

#### **4.5 Determination of the Sample Size**

The sample size for this study is not determined based on hypothesis testing considerations. A minimum of 45 evaluable (15 per cohort) subjects will be needed. This is based on an assumed response rate for reaching the top infusion parameter for each endpoint of 50% (i.e., 100 mL/h for the Pump-Assisted Flow Rate Cohort, 50 mL per injection site for the Pump-Assisted Volume Cohort, and 2 mL/min for Manual Push Flow Rate Cohort). Using a binomial distribution with 15 evaluable subjects, there will be a 94% probability that the observed response rate for a single endpoint in the study is  $\geq 33\%$ .

#### **4.6 Planned Interim Analyses and Reviews**

##### **4.6.1 Interim Analyses Other Than Sample Size Re-estimation**

No formal interim analysis will be performed. Safety and IgG data will be examined by the study team in an ongoing fashion while the study is being conducted.

##### **4.6.2 Interim Sample Size Re-estimation**

Sample size re-estimation is not planned for this study.

### **5 Changes in the Conduct of Planned Analyses**

Changes in the conduct of the analysis as compared to the most recent protocol or protocol amendments will be covered in the SAP. Changes in the conduct of the analysis after the finalization of the SAP will be covered by a SAP amendment. All changes in the analysis as compared to the protocol or protocol amendments will be described in the CSR. Any post hoc analyses after database lock will clearly be labelled as post hoc.

There will be a separate column "Missing" in the AE summary tables if the assessment for severity is missing. Missing severity will not be imputed as "Severe" as stated in the protocol.

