9.2 Severity of Adverse Events

The severity of each AE (ie, nonserious and serious AEs) is to be assessed by the investigator as follows:

Severity	Definition
Mild	A type of AE that is usually transient and may require only minimal treatment or therapeutic intervention. The event does not generally interfere with usual activities of daily living.
Moderate	A type of AE that is usually alleviated with additional specific therapeutic intervention. The event interferes with usual activities of daily living, causing discomfort but poses no significant or permanent risk of harm to the subject.
Severe	A type of AE that interrupts usual activities of daily living, or significantly affects clinical status, or may require intensive therapeutic intervention.

CDISC SDTM Severity Intensity Scale for Adverse Event Terminology.

AE = adverse event.

If AE severity is not reported (missing), it will be conservatively assessed as a severe AE.

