### 8.1 Missing Data

#### 8.1.1 Imputation of Non-Date Missing Data

Missing data occurs when any requested data is not provided, leading to blank fields on the collection instrument. These data will be indicated by the use of a “blank” in subject listing displays. Answers such as “Not applicable” and “Not evaluable” are not considered to be missing data and should be displayed as such.

Subjects with the designation of treatment relationship for AEs and serious AEs (SAEs) missing will have the worst realistic case assumed to impute the relationship: if relationship to study treatment is missing and the AE started on or after the first infusion of study treatment it will be assumed to be “Related” (worst case). If the AE with missing relationship to treatment started before the first infusion of study treatment, it will be considered as “Not Related” (realistic case). There will be no other imputation for missing data.

For variables which determine the proportion of subjects, all subjects in the SAF will be included in the denominator when calculating the percentages irrespective of whether their outcome may be missing.

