Each AE summary table will present the number of subjects, percentage of subjects based on the SAF, number of events, and AE rate per infusion.

One overview summary of TEAEs table with entries for:

- any TEAE;

- causally related TEAEs;
- temporally associated TEAEs within 72 h;
- causally related or temporally associated TEAEs within 72 h
- deaths;
- causally related deaths;
- serious TEAEs;
- causally related serious TEAEs;
- study discontinuation due to TEAE;
- causally related study discontinuation due to TEAE;
- study drug withdrawal due to TEAE;
- causally related study drug withdrawal due to TEAE;
- local TEAEs;
- causally related local TEAEs;
- maximum severity of TEAEs.

will be produced.

The following summary tables of TEAEs will be produced:

- by SOC and PT;
- SAEs by SOC and PT;
- by SOC, PT, and maximum severity (missing severity will be presented as separate category);
- by SOC, PT, and causality (missing causality will be considered “Related” as outlined in Section [8.1.1](#));
- by SOC and PT temporally associated within 72 hours after treatment;
- by SOC and PT causally related or temporally associated within 72 hours after treatment;

- time to onset of TEAEs (descriptive statistics and categories 0 days, 1 day, 2 days, 3 days, > 3 days);
- duration of TEAEs (descriptive statistics and categories 1 day, 2 days, 3 days, > 3 days);
- tolerability of the infusion parameter (number of infusions without severe local reactions / number of all infusions).

Time to onset of TEAE will be calculated as

TEAE start date and time – infusion start date and time.

For the categories, the time will be rounded to days.

Duration of TEAEs will be calculated as defined in Section 8.2.3.

Tolerability of a certain infusion parameter within a cohort will be calculated as

number of infusions without severe local reactions / number of infusions

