and will be presented by infusion parameter and cohort. The number of infusions irrespective of their validity as defined in Section 11.1 will be used as denominator for the assessment of tolerability. The total number of infusions within infusion parameter level and within cohort will be considered as denominator for the tolerability within infusion parameter level and within cohort, respectively. An infusion without severe local reactions is defined as no occurrence of a severe local reaction from the start date and time of an infusion until the start date and time of the next infusion or study end if this was the last infusion.

Local TEAEs will be identified by the MedDRA high level terms “administration site reactions NEC”, “infusion site reactions”, and “injection site reactions”. The MedDRA high level terms will be reviewed prior to database lock and the list of terms to be included into Local TEAEs will be updated. Local TEAEs will be included in all tables by using a virtual SOC called “Local Adverse Events”. In addition, the local TEAEs will also be presented by their MedDRA SOC “General disorders and administration site conditions”.

TEAEs will be sorted in descending order of total incidence by SOC and PT.

The summary will report for the Any TEAE row, each SOC, and each PT, the number of subjects with at least one TEAE, counted for the maximum reported severity in the table by severity. Local TEAEs will be reported only once in the Any row.

A listing of MedDRA SOC, PT, and verbatim text will be provided.

All AEs will be listed. TEAEs will be listed for the SAF. Other AE listings will use all available data. The listings will include the variables as specified in Section 7 and in addition MedDRA SOC, PT, and the verbatim, AE start and end date and time if available, duration of AE in days, severity, serious (yes or no), relationship to treatment (yes or no), outcome, action taken, and AE flags (TEAE, SAE, temporal relationship within 72h [AE72h]). Additionally, a listing of subject IDs for each individual PT will be produced.

The following listings will be provided:

- Non-TEAEs – all available data;
- TEAEs – SAF;
- Deaths – all available data;
- SAEs – all available data;
- AEs leading to study discontinuation – all available data;
- Local TEAEs – SAF;
- MedDRA SOC and PT with all AE verbatim – all available data;
- Subject IDs for each PT – all available data.

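### The SAP drops the protocol's missing-means-severe rule without addressing tolerability, where, as written, ungraded local reactions count in its favour

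*SAP*

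**What the plan says.** Protocol 9.2 sets the default: "If AE severity is not reported (missing), it will be conservatively assessed as a severe AE". SAP 5, the section for departures from the protocol, withdraws it. It states "Missing severity will not be imputed as" severe and provides a separate column "in the AE summary tables if the assessment for severity is missing". It gives no reason. SAP 11.4 repeats the display rule for the table by maximum severity: "missing severity will be presented as separate category". SAP 8.1.1 gives a worst-case rule for missing causality and then closes the list: "There will be no other imputation for missing data".

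Tolerability is a secondary endpoint (protocol 2.2.2, SAP 4.2). SAP 11.4 calculates it as "number of infusions without severe local reactions / number of infusions". On the numerator it says: "An infusion without severe local reactions is defined as no occurrence of a severe local reaction", with a window that runs from the start of one infusion to the start of the next, or to study end. On the denominator it says: "The number of infusions irrespective of their validity as defined in Section 11.1 will be used as denominator for the assessment of tolerability". SAP 2.2 carries the same definition.

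**The concern.** A separate category for missing grades works in a table with several severity levels. Tolerability has only two outcomes per infusion and no third place for an unknown. Once the imputation is withdrawn, an ungraded local reaction has to fall on one side, and the definition puts it on the favourable one. The declared change therefore alters a secondary endpoint that SAP 5 does not mention, and it can do so in one direction only.

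The SAP stays cautious about other missing AE attributes. Missing causality after the first infusion becomes related (8.1.1). AEs with missing start dates are assumed treatment-emergent unless there is clear evidence otherwise (11.4). Missing end dates of resolved events are filled so as not to understate duration (8.1.2). Severity, the attribute that defines tolerability, is the one that loses its cautious default. At stake is how the tolerability percentages at the higher infusion levels are read in an open-label study without a control group.

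**Working it through.** **No plan figure to reproduce.** The documents give no expected tolerability and no expected number of missing grades. Their one design probability, 94% for at least 5 responders of 15 at a true rate of 50%, reproduces as 0.9408, but this point does not depend on it.

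**Following one infusion through the SAP.** Take an infusion followed by a single local reaction with no severity recorded.
1. Is the reaction severe? Under protocol 9.2, yes. Under SAP 5 it is not made severe, and 8.1.1 allows no other imputation.
2. Did a severe local reaction occur in the window? Under the SAP, none is on record.
3. Is the infusion excluded? No. The denominator is all infusions, and no rule removes those with an ungraded reaction.
4. The infusion therefore enters the numerator as free of severe local reactions.

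**Formula.** Let N be the infusions at a level, s those with a graded severe local reaction, and m those with an ungraded local reaction and no graded severe one.
- Protocol rule: (N − s − m)/N
- SAP as written: (N − s)/N
- Difference: m/N, which is never negative

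**Inputs.** 15 subjects per cohort (protocol 11.1, SAP 4.5). Four pump infusions per subject per level (SAP 2.2). Manual push: 8 to 28 scheduled infusions per subject per level (SAP Table 3). The values of m are assumed for illustration, and s is set to 0.

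| Setting | N | Points per affected infusion | Protocol-rule tolerability, m = 1 / 3 / 5 |
|---|---|---|---|
| Full pump level | 15 × 4 = 60 | 1.67 | 98.3% / 95.0% / 91.7% |
| Top pump level, half the cohort (assumed) | 7.5 × 4 = 30 | 3.33 | 96.7% / 90.0% / 83.3% |
| Top pump level, 5 subjects (assumed) | 5 × 4 = 20 | 5.00 | 95.0% / 85.0% / 75.0% |
| Full manual push level, all twice weekly | 15 × 8 = 120 | 0.83 | 99.2% / 97.5% / 95.8% |
| Full manual push level, all seven times weekly | 15 × 28 = 420 | 0.24 | 99.8% / 99.3% / 98.8% |

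The SAP as written gives 100% in every cell. The row with 30 infusions takes the 50% response rate assumed for the top level as the share of subjects infused there. Subjects who try the top level and do not respond are infused too, so under that design assumption N would be at least 30 and the effect per infusion at most 3.33 points. The row with 20 infusions goes below that assumption, to the 5 subjects needed to meet the success criterion.

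**The case against.** The change is declared in the proper section. SAP 3 says decisions were made before database freeze, and SAP 5 requires changes to be described in the clinical study report. A reader might infer a concealed relaxation or an accidental contradiction; the documents support neither.

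No SAP sentence states outright how an ungraded reaction enters tolerability. The table shells are a separate document, and tolerability is listed among the TEAE summary tables, for which the separate column is promised. This stands in part: the result is inferred. But it follows from the definition, the denominator and the closed imputation list together, and an extra column would not change how the proportion is calculated.

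The information is not lost. The local TEAE listing carries severity and start dates and times, so the figure could be recomputed. This stands, but it leaves the reported endpoint as it is.

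Missing grades should be few. The investigator must grade every AE (protocol 9.2), and questionable data are queried (protocol 14.5.2). This also stands, and it limits the expected size.

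Finally, protocol 1.4 reports that 99% of AEs in the pivotal studies were mild or moderate, so counting an unknown as severe will often misclassify it. This is fair, and it is a reason to show both values. It does not justify leaving unaddressed a default that can only favour the product.

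**Conclusion.** The point holds for one secondary endpoint. As written, the SAP rule gives a tolerability equal to or higher than the protocol rule would. The direction is certain under the SAP's definitions; the size is not. It is m/N, where m is unknown and possibly zero. Only local reactions matter, and only when no graded severe local reaction falls in the same window.

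Three stronger readings are tempting and not supported:
- **That the label decision is affected.** The recommended level depends only on a responder rate of at least 33% (protocol 11.3.5, SAP 11.1), and the criteria for a valid infusion do not use AE severity.
- **That tolerability carries the safety case for each level.** It is one of six unranked secondary endpoints and has no threshold attached.
- **That the count of infusions not tolerated would about double.** This needs an assumed 1% of missing grades, and it carries the severity mix of all AEs in earlier studies over to local reactions per infusion here. Even with a local reaction after every infusion, 1% of 60 is 0.6 infusions, or 1 point.

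The protocol's statement in 11.3.5 that missing data will not be imputed belongs to the infusion-parameter analysis and does not cancel the AE rule in 9.2.

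**What to change.** Keep the separate column for missing severity in the AE tables. In SAP 2.2 and 11.4, add that for tolerability a local reaction with missing severity counts as severe, as in protocol 9.2. Report the value with missing treated as not severe as a sensitivity line, and adjust SAP 5 to say that the change applies to the display of AE severity and not to tolerability.

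The cost is a sentence or so through a SAP amendment, a route SAP 5 already provides, and one extra line of output. The downside is that tolerability may read slightly lower and some mild or moderate reactions may be counted as severe; the sensitivity line shows by how much. If no grades are missing, no result changes.

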## 6 Study Analysis Sets

### 6.1 Screened Analysis Set

The Screened Analysis Set (ScAS) will comprise all subjects who provided written informed consent and who undergo study screening procedures.

### 6.2 Full Analysis Set

The Full Analysis Set (FAS) will comprise all subjects who provided written informed consent and who are included in the study, i.e. who undergo study procedures after Screening. Screening failures will not be included in the FAS.

### 6.3 Safety Analysis Set

The Safety Analysis Set (SAF) will comprise all subjects in the FAS who received at least 1 dose or a partial dose of IgPro20 in the study.

## 7 General Considerations

### Database Format

Datasets will be provided in Study Data Tabulation Model (SDTM) format. Analysis datasets will be created according to Clinical Data Interchange Standards Consortium standards.

For each subject, data up to the time of study completion, loss to follow-up, or withdrawal from study, whichever is latest, will be included in the appropriate analysis sets defined in Section 6. If a subject withdraws consent, the subject's data will only be used until the time when consent is withdrawn.

### Statistical Analysis System (SAS) Version

SAS version 9.3 or higher will be used to perform all data analyses and to generate TFLs.

### Reporting Standards for Continuous and Categorical Variables

Continuous variables will be summarized in terms of the number of observations, mean, standard deviation (SD), median, first quartile, third quartile, minimum, and maximum. Other descriptive statistics (e.g., 95% confidence intervals [CIs]) may be reported when appropriate. Categorical variables will be summarized using frequency counts and percentages. Missing values will be presented as separate category. Percentages will be based

on the non-missing values. Analyses that use other descriptive statistics will have the specific descriptive statistics required identified with the analysis in the applicable SAP section.

**TFLs Format**

All ICH required data in the database will be presented in data listings.

Data will be displayed as described in this SAP and in the supporting, separate TFL shells document(s).

Tables will be presented by cohort and infusion parameter within cohort (Pump-Assisted Volume: Volume per Site 25 mL, 40 mL, 50 mL, and Total; Pump-Assisted Flow Rate: 25 mL, 50 mL, 75 mL, 100 mL, and Total; and Manual Push Flow Rate: 30 mL/h [0.5 mL/minute], 60 mL/h [1 mL/minute], 120 mL/h [2 mL/minute], and Total) as specified in the respective sections. As subjects may participate in more than one infusion parameter group, the total column may not be the sum of the infusion parameter columns. Subjects and events will be counted once in the total column. Events and assessments will be assigned to the infusion parameter level under which they occur. There will be total columns within cohorts, but no total column over cohorts. Details will be specified in the TFL shells document and in the corresponding SAP section.

Listings will include cohort and infusion parameter, site number, subject number, and basic demographics (age, sex, BMI at Screening). Events and assessments will be assigned to the infusion parameter under which they occurred or were assessed. In subject-level listings, the subjects will be assigned to the highest infusion parameter which they successfully reached. Listings will be presented for a specific analysis set or for all available data depending on the nature of the information listed. In the listings for all available data, a column will be inserted showing the smallest analysis set the subject is assigned to (hierarchy of analysis sets in terms of size/subset: SAF  $\leq$  FAS  $\leq$  ScAS, analysis sets may comprise the same subjects).

Unless otherwise stated, listings will be sorted by treatment status (not treated subjects followed by treated subjects), and within treatment status by cohort and infusion parameter, site-subject number, and by visit date and time or by event date and time. In case of partial dates, date sorting will be by year, month, and day. If any of these variables does not apply to a listing, then that listing will use only those variables which are applicable in the order given here.

Unless otherwise stated, summary tables including figures will be reported by cohort and infusion parameter. The cohort/infusion parameter will be labelled as specified in Section 0. Tables presented by cohort and infusion parameter may contain a total column or block.

If there is no data available for a table or listing (e.g., no deaths occurred in the study), the planned output will be displayed as “No data to report”.

